10.8.6. Efficacy Assessments

Anthropometric measurements cannot be undertaken in the participant's home. Administration of PRO/ObsRO and blood draws may be undertaken by home health teams.

10.8.7. Independent Oversight Committees

The eDMC will continue to meet via teleconference in accordance with the eDMC charter.

10.9. Appendix 9: Abbreviations

The following is a list of abbreviations that may be used in the protocol.

Abbreviation	Term
Abs	absolute
ADA	anti-drug antibodies
ADE	adverse device effect
AE	adverse event
AESI	adverse events of special interest
ALT	alanine aminotransferase
ANOVA	analysis of variance
AST	aspartate aminotransferase
AUC	area under the concentration-time curve
AUC ₀₋₁₆₈	area under the concentration-time curve from time 0 to 168 hours
AUC _{last}	area under the concentration-time curve from 0 to time of last measurable concentration
AUC _{inf}	area under the concentration-time curve from time 0 to infinity
AUC _{tau}	area under the concentration-time curve at steady state over the dosing interval t
AV	atrioventricular
β-hCG	beta-human chorionic gonadotropin
BIW	twice weekly
BMI	body mass index
BP	lood pressure
BUN	blood urea nitrogen
CFR	Code of Federal Regulations
CHAQ	Childhood Health Assessment Questionnaire
CIOMS	Council for International Organizations of Medical Sciences
CK	creatine kinase
CL/F	apparent clearance of drug from eg, plasma
C _{max}	maximum observed concentration
CO ₂	carbon dioxide (bicarbonate)
COA	Clinical Outcome Assessment
CCI	[REDACTED]
CONSORT	Consolidated Standards of Reporting Trials
CCI	[REDACTED]
CRF	case report form
CRO	contract research organization
CSF	cerebrospinal fluid
CSR	clinical study report
CT	clinical trial
CCI	[REDACTED]

Abbreviation	Term
DILI	drug-induced liver injury
DNA	deoxyribonucleic acid
DRE	disease-related event
DU	dispensable unit
EC	ethics committee
ECG	electrocardiogram
eCRF	electronic case report form
eDMC	external data monitoring committee
EDP	exposure during pregnancy
EMA	European Medicines Agency
ENT	Ear nose and throat
EQ-5D	EuroQol- 5 dimensions
EQ-VAS	EuroQoL- visual analogue score
EU	European Union
EudraCT	European Union Drug Regulating Authorities Clinical Trials (European Clinical Trials Database)
FDA	Food and Drug Administration
FGF	Fibroblast growth factor
FGFR3	Fibroblast growth factor receptor 3
FIH	first-in-human
GCP	Good Clinical Practice
GGT	gamma-glutamyl transferase
GLP	Good laboratory practice
HIPAA	Health Insurance Portability and Accountability Act
HRQL	health-related quality of life
IB	investigator's brochure
ICD	informed consent document
ICH	International Council for Harmonisation of Technical Requirements for Pharmaceuticals for Human Use
ID	identification
IGF-1	Insulin-like growth factor 1
IMP	investigational medicinal product
IND	investigational new drug
INR	international normalized ratio
IP	investigational product
IPM	investigationalp manual
IPAL	Investigational Product Accountability Log
IRB	Institutional Review Board
IRT	Interactive Response Technology
ISR	injection site reaction
LFT	liver function test
MAD	multiple ascending dose

Abbreviation	Term
MCH	mean corpuscular hemoglobin
MCHC	mean corpuscular hemoglobin concentration
MCV	mean corpuscular volume
NDCMC	newly diagnosed chronic medical condition
Msec	millisecond
N/A	not applicable
Nab	neutralizing antibodies
CCI	[REDACTED]
NDCMC	Newly diagnosed chronic medical condition
NIMP	noninvestigational medicinal product
NOAEL	no-observed-adverse-effect level
NPRB	Natriuretic peptide receptor B
ObsRo	Observer report outcome
OLE	Open-label extension
CCI	[REDACTED]
PBMC	peripheral blood mononuclear cell
PCRU	Pfizer clinical research unit
PD	pharmacodynamic(s)
PFS	prefilled syringe
PGIC	Patient global impression of change
PGIS	Patient global impression of severity
PI	principal investigator
PK	pharmacokinetic(s)
PKCP	PK study cohort parameter
PopPK	Population pharmacokinetics
PRO	Patient-Reported Outcome
CCI	[REDACTED]
PSG	polysomnography
PT	prothrombin time
QoLISSY Brief	Quality of Life in Short Stature Youth Brief
QTc	corrected QT
QTcF	QTc corrected using Fridericia's formula
QW	Once Weekly
R _{AC}	accumulation ratio based on AUC (observed)
RBC	red blood cell
RNA	ribonucleic acid
SAE	serious adverse event
SAD	single ascending dose
SaO ₂	oxygen saturation
SAP	statistical analysis plan
SAR	Serious Adverse Reaction
SC	subcutaneous

Abbreviation	Term
SoA	schedule of activities
SOP	standard operating procedure
SRSD	single reference safety document
SUSAR	suspected unexpected serious adverse reaction
T _{1/2}	terminal phase half-life
TA-46	Previous name for reciferecept
TBili	total bilirubin
TEAE	treatment-emergent adverse event
T _{max}	time to reach C _{max}
ULN	upper limit of normal
US	United States
WBC	white blood cell
WOCBP	woman/women of childbearing potential

10.10. Appendix 10: Subcutaneous Dosing Instructions

SUBCUTANEOUS DOSING INSTRUCTIONS

GENERAL INSTRUCTIONS

- Allow prepared syringes with the medication to reach room temperature for 15 minutes prior to administration (they should not be cold to touch);
- Never reuse needles or syringes;
- Dispose of all used materials in the appropriate sharps container and return used vials into the cartons to be checked by a study monitor.

Gather your supplies:

- Alcohol pads;
- Prepared syringe with medication;
- Puncture resistant sharps container.

[figure not shown]
Choose one of the recommended injection sites described below:

The injection(s) should be given when participant is sitting or lying down into the **abdomen or outer thighs**. **The back of the arms may be used as an alternative injection site (Figure 2).**

Do not inject into areas where the skin is tender, bruised, red, or hard. Avoid areas with scars, moles and avoid the area 1 inch from the naval.

- Injections should start in either the abdomen or outer thighs at number one and proceed in a clockwise manner from site number 1 through to number 4.
- If injections are given in the back of the arms, alternate between the left and right arms.
- For each injection given (including if two injections are needed for one dose), a new injection site must be chosen. Inject at least 2 inches from the previous site.

[figure not shown]
Figure 2. Injection Site Rotation

Preparing the subcutaneous injection site and injecting Recifercept

[figure not shown]
1. Wash hands thoroughly with soap and water prior to any injections.
2. Choose the site from Figure 2 and clean the site where Recifercept is to be injected with a new alcohol swab, using a circular motion, starting from the inside and working to the outside of the chosen injection site. Allow the area to dry thoroughly, do not blow the area dry. DO NOT touch this area again before giving the injection.
3. Using the thumb and forefinger, lift up a fold of skin with one hand (Figure 3).

Figure 3. Technique for Holding Skin Prior to Injection

[figure not shown]
1. With the other hand, hold the syringe like a pencil with the bevel up. With a quick, short motion, push the needle into the skin at an angle of 45° (Figure 4).

Figure 4. Injection Angle

1. Once the needle has been pushed into the skin, release the pinched skin while still holding the needle in place. With your free hand, push the plunger all the way down at a slow, steady rate to deliver the entire contents of the syringe Figure 5).

Figure 5. Technique for Injecting Study Intervention

1. When the syringe is empty, remove the needle from the skin; be careful to keep it at the same angle it was when it was inserted into the skin. Place the syringe/needle in the sharps container provided.
2. Repeat steps 1 through 5 if a second syringe is required for the total dose.
3. Slight bleeding may occur. Cover with a sterile gauze pad if needed. DO NOT rub the injection site. You may place a band aid over the injection site.

1. VERSION HISTORY

Table 1. Summary of Changes

Version/ Date	Associated Protocol Amendment	Rationale	Specific Changes
1 21 Dec 2020	1 09 Nov 2020	N/A	N/A
2 16 Aug 2022	3 23 Mar 2022	Addition of PK cohort; Clinical Outcome Assessment changes	
Added specification and analysis of (Primary) PK endpoints (Section 3.1.1 & Section 6.1.2)Added 2 analysis sets to accompany the PK cohort (Section 4)Added language on CHAQ data (Section 5.3.2)Futility language removed (Section 7.1)

2. INTRODUCTION

This statistical analysis plan (SAP) provides the detailed methodology for summary and statistical analyses of the data collected in Study C4181005. This document may modify the plans outlined in the protocol; however, any major modifications of the primary endpoint definition or its analysis will also be reflected in a protocol amendment.

2.1. Study Objectives, Endpoints, and Estimands

Objectives	Estimands	Endpoints
Primary:	Primary:	Primary:

Evaluate the safety and tolerability of recifercept doses and dosing regimes in participants aged ≥ 2 to < 11 years with achondroplasia.To assess efficacy of recifercept to increase height growth in children with achondroplasia.	
N/A
 
The primary efficacy estimand is intended to provide a population level estimate of the effect of recifercept on a continuous endpoint. 
Population-level summary: ratio between participants in the trial and a reference population [Merker et al, 2018]¹ in growth of height at 12 month; ratio between treated and reference population is observed change-from-baseline of treated participants standardized by reference participant given age and gender.
	
Safety and tolerability of recifercept as assessed through frequency and severity of AEs/SAEs.
 
Increase in height growth above expected in reference population [Merker et al, 2018]¹
Secondary:	Secondary:	Secondary:

To evaluate the pharmacokinetics (PK) of recifercept in children aged ≥ 2 to < 11 years old with achondroplasia.To assess efficacy of recifercept to improve achondroplasia-related complications.		
Population PK characterization in children aged ≥ 2 to < 11 years old with achondroplasia. Clearance (CL/F) and other PK parameters of recifercept to assess exposures in different age group.
 
Sitting height/standing height ratio.Arm span to height/length difference.Knee height:lower segment ratio.Occipito-frontal circumference.

Objectives	Estimands	Endpoints
		
 Ratio of occipito-frontal distance to occipito-mid-face measurements. z-score of the above proportionality and skull morphology where achondroplasia reference datasets exist (occipito-frontal circumference, arm span, sitting height). Fixed flexion angles at elbow. Polysomnography parameters in those with pre-existing sleep-disordered breathing at the time of enrollment. Body mass index (BMI). Waist:chest circumference ratio. Change from baseline in CHAQ component and index scores, QoLISSY Brief total score.

 Assess change in individual safety parameters. 		
 Change from baseline in safety labs, vital signs, physical examination. Rate of anti-drug antibodies.
CCI		

2.1.1. Primary Estimand(s)

The primary estimand is defined according to the primary objective and is in alignment with the primary endpoint. It includes the following 4 attributes:

- Population: Patients with achondroplasia, as defined by inclusion/exclusion criteria;
- Variable: Height Growth at 12 months;
- Height Growth = (Observed Change from Baseline in standing height (cm))/(Expected Change from Baseline (cm)[Merker et al, 2018]¹)

- Intercurrent event(s): Withdrawal and all events leading to missing data will be excluded from efficacy analysis and will not have their data imputed;
- Population-level summary: Mean Height growth at 12 months adjusted for age and gender.

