9.1.1. Estimands

The primary efficacy estimand will be the population treatment effect of the mean change-from-baseline of a continuous response (ie, height growth) at month 12 irrespective of IP compliance. Increase in height growth above expected growth in reference population, a co-primary endpoint, is defined as the height growth in the achondroplasia reference population +50%. Intercurrent event for the efficacy estimand: withdrawal and all events leading missing data will be excluded from efficacy analysis and will not have their data imputed. The population-based treatment effect will be the mean change-from-baseline at 12 months.

The secondary estimand will be the population treatment effect of the mean change from baseline of a continuous response, defined as the decline in the difference of arm span to standing height. Intercurrent event for the efficacy estimand: withdrawal and all events leading missing data will be excluded from efficacy analysis and will not have their data imputed.

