4. ANALYSIS SETS (POPULATIONS FOR ANALYSIS)

Data for all participants will be assessed to determine if participants meet the criteria for inclusion in each analysis population prior to unblinding and releasing the database and classifications will be documented per standard operating procedures.

Population	Description
Full Analysis Set (FAS)/Safety	All participants receiving at least one dose of reciferecept. Participants will be analyzed according to the dose they actually received.
Per-Protocol Analysis Set (PPAS)	All participants receiving at least one dose of reciferecept and have complete data at baseline through month 12 and without protocol deviations that were thought to impact the efficacy evaluation during the treatment period. Participants will be analyzed according to the randomized intervention.
PK Concentration set	All participants who received at least one dose of reciferecept and have at least one evaluable concentration.
PK Study Cohort	All participants who received a dose of the reciferecept Phase 2 formulation and a dose of the Phase 3 formulation with at least one evaluable concentration result.

Population	Description
PK Study Cohort Parameter (PKCP)	All participants in the PK cohort who have at least one PK parameter of interest.

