6. ANALYSES AND SUMMARIES

6.1. Primary Endpoint(s)

6.1.1. Increase in height growth above expected in reference population

6.1.1.1. Main Analysis

- Estimand strategy: Hypothetical ([Section 2.1.1](#)).
- Analysis set: FAS ([Section 4](#)).
- Analysis methodology: Change from baseline relative to Merker (2018) will be analyzed using MMRM including data from Months 3, 6, 9, and 12 with gender (and possibly age) as a covariate, subject (and/or time) as a random effect and an unstructured covariance matrix ([Section 5.2.1](#)).
- Intercurrent events and missing data: Data after study drug discontinuation and rescue will be excluded; intermediate missing values will not be imputed.
- The sample size, mean, standard deviation, median, minimum, and maximum at the baseline and postbaseline visits for observed standing height and change from baseline will be presented for each treatment arm.
- The least-squares (LS) means, the 95% confidence interval for the LS means, the difference between the LS means for each pair of treatment groups, and the corresponding 95% confidence interval will be presented for change from baseline in standing height for all postbaseline visits.

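### The documents give incompatible rules for the heights of children who withdraw, and two of them amount to a completers analysis of the primary endpoint

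*SAP*

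**What the plan says.** Four rules apply to the same child, one who starts treatment and withdraws before Month 12.

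- **Estimand text.** SAP 2.1.1: "Withdrawal and all events leading to missing data will be excluded from efficacy analysis and will not have their data imputed". SAP 2.1.2 repeats this for arm span to height. Protocol 9.1.1 has the same rule for both estimands ("withdrawal and all events leading missing data will be excluded from efficacy analysis"), and the Synopsis has it for height. Protocol 9.1.1 also defines the effect as "irrespective of IP compliance".
- **Protocol model.** Sections 9.4.2 and 9.4.3 specify an ANOVA of the 12-month change by dose group. The FAS is the primary population and the per-protocol set (PPAS) is for sensitivity.
- **SAP main analysis.** Section 6.1.1.1 is labelled "Estimand strategy: Hypothetical", cites 2.1.1, uses the FAS ("All participants receiving at least one dose of reciferecept"), and "will be analyzed using MMRM including data from Months 3, 6, 9, and 12". It removes only measurements made after study drug is stopped or rescue begins. Section 6.2.1.1 (arm span) and 7.2 (interim) carry the same data rule.
- **SAP Appendix 1.** For the same FAS main analyses, all collected data stay in whatever intercurrent events occur.

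**The concern.** A child who leaves after Month 6 is out of the analysis under the estimand text and has no usable outcome under the protocol ANOVA. The same child contributes Months 3 and 6 under SAP 6.1.1.1. Under Appendix 1, any height taken after stopping drug would count as well. Someone working from the estimand or the protocol model could produce a different primary estimate from someone working from SAP 6.1.1.1, and each could cite the documents.

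The difference matters because each dose is compared with a published reference, not a concurrent arm, so no similar dropout on the other side can offset selection. If slower growers are likelier to leave, the mean ratio among those who remain is too high. Protocol 7.1 says a child who definitively stops treatment leaves the study, so such children have no Month 12 height. (Section 7.2.1 reads differently for families who ask to stop treatment; the two sections need reconciling.) Non-compliance is a listed reason for stopping, so excluding these children also sits badly with an effect defined without regard to compliance.

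**Working it through.** **1. Inputs from protocol 9.2.** 54 children randomized, 18 per dose, to obtain 15 per dose. One-sided alpha 0.05/3 = 0.017. Variability 0.15, whose scale is not stated; taken here as the SD of observed/expected growth. Target: 50% above reference, a ratio of 1.5 against 1.0.

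**2. The plan's own power.** One-sample t-test, noncentrality (0.5/0.15) × √n. With n = 15 this is 12.9 and power is about 100%. With n = 18 it is 14.1, again about 100%; even n = 4 gives 96%. The stated figure of over 90% holds under either rule.

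**3. Room for disagreement.** 18 − 15 = 3 per dose (16.7%), or 9 of 54. This is an upper limit: a child with no post-baseline height adds nothing under either rule.

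**4. Direct calculation.** Suppose the 3 withdrawn children grow k SDs less than the 15 who stay.

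- Bias of the completers mean = k × 0.15 × 3/18.
- If the true mean over all 18 is 1.0, the test on 15 (SD 0.15, t with 14 df, critical value 2.35) has noncentrality k × √15/6.

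| k | Bias | Chance of a false positive (nominal 0.017) |
|---|---|---|
| 0.5 | 0.0125 | 0.034 |
| 1.0 | 0.025 | 0.064 |
| 1.5 | 0.0375 | 0.110 |
| 2.0 | 0.050 | 0.176 |

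**5. Simulation with an explicit withdrawal mechanism.** Assumed: true ratio 1.0; Month 12 SD 0.15; height measurement error SD 0.3 cm; expected growth 4 to 6 cm per year; 3 of 18 lost per dose. Completers are tested with the SD pooled over doses. The comparator is the maximum-likelihood Month 12 mean, equivalent to an unstructured MMRM.

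| Withdrawal | Completers bias | Completers type I error | MMRM-type estimate |
|---|---|---|---|
| Unrelated to growth | none | about 0.017 | unbiased, standard error about 4–7% smaller |
| Odds × 2.7 per 0.15 lower Month 9 ratio | about +0.02 | 0.055–0.064 | bias under 0.001, error about 0.015–0.018 |
| Three slowest at Month 6 or 9 leave | +0.027 to +0.037 | 0.09–0.17 | bias under 0.001, error about 0.015–0.018 |

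Reruns with separate code agree to within simulation error. A different set-up (loss after Month 6, visit correlation 0.5 to 0.8) gave smaller completers biases, 0.007 to 0.019. At a similar bias, the error rate in step 5 exceeds that in step 4 because removing slow growers also shrinks the observed SD and pooling lowers the critical value.

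**6. Summary range.** The largest simulated bias corresponds to k = 0.037 × 6/0.15 = 1.48, so the k = 2 row goes beyond even the three slowest leaving and is left out. That gives a bias of about +0.01 to +0.04 and a type I error of about 0.03 to 0.17.

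**The case against.** The best defence is that the plan names one main population. Protocol 9.4.2, SAP 6.1.1.1 and SAP Appendix 1 all say FAS, and the set requiring complete data to Month 12 (the PPAS) is for sensitivity only. The estimand sentence can also be read as excluding data after the event, which would fit SAP 6.1.1.1. This stands to a degree: a programmer following the SAP would run the FAS model.

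It does not remove the conflict. The plain text of the estimand removes withdrawals, and the protocol ANOVA reaches the same end by another route, since without imputation it needs a Month 12 height. Protocol section 9 says major changes to the primary analysis will also appear in a protocol amendment, yet the protocol still specifies the ANOVA. The reconciling reading does not cover Appendix 1 either.

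A second objection is that the size is conditional. This stands in full. The documents give no withdrawal mechanism, height error or expected annual growth, and losing the three slowest children in a dose group is close to a worst case. The near-zero MMRM bias follows from letting withdrawal depend only on growth already observed. It describes an unstructured model estimating the Month 12 mean; the Appendix 4 code has no dose-by-month term and requests dose means averaged over months, so the result does not carry over to that code.

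**Conclusion.** The inconsistency is established from the text. It leaves the primary estimate, and the arm span estimate, dependent on which section is followed.

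A reader might infer that the plan designates two rival primary populations, or that its primary analysis is completers-only. The documents do not support that: the FAS is the named main set throughout, and a completers result arises only through the estimand wording or the protocol ANOVA. Nor is an inflated error rate established. The range of 0.03 to 0.17 against 0.017, with a bias of +0.01 to +0.04, assumes growth-related loss of 3 of 18 per dose and an SD of 0.15 on the ratio scale. With withdrawal unrelated to growth the bias is nil. The SAP's approach protects against it only if withdrawal depends on observed growth. The issue is selection bias and an ambiguous primary estimate. It should be corrected before the primary analysis.

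**What to change.** Adopt one rule and change all the affected text together.

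1. In protocol 9.1.1, the Synopsis, and SAP 2.1.1 and 2.1.2, replace the exclusion sentence with: *Participants who withdraw remain in the efficacy analysis with all height (or arm span) measurements taken up to withdrawal, including the early-termination measurement if it falls within the data rule of SAP 6.1.1.1; later missing visits are not imputed and are handled by the MMRM under a missing-at-random assumption.*
2. In protocol 9.4.2 and 9.4.3, replace the Month 12 ANOVA with the SAP's FAS MMRM. Without this, step 1 would create a new contradiction inside the protocol.
3. Make the data rules in SAP 6.1.1.1, 6.2.1.1, 7.2 and Appendix 1, the hypothetical-strategy label, and the protocol's compliance clause express the same strategy. The rule should say plainly whether an early-termination height counts.
4. Keep completers in the PPAS sensitivity analysis only.

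The cost is wording in both documents, including a protocol amendment. Heights are already scheduled every three months, so nothing new is collected. The estimate may be slightly less favourable than a completers mean.

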2.1.2. Secondary Estimand(s)

The secondary efficacy estimand comprises the following 4 attributes:

- Population: Patients with achondroplasia, as defined by inclusion/exclusion criteria;
- Variable: Change from baseline to 12 months in the difference between arm span (cm) and standing height (cm);
- Intercurrent event: Withdrawal and all events leading to missing data will be excluded from efficacy analysis and will not have their data imputed;
- Population-level summary: Mean change-from-baseline of arm span/standing height difference at 12 months adjusted for age and gender.

